1.0 SYNOPSIS

Title:	Practical Evaluation of Fractional Flow Reserve (FFR) and its Associated Alternate Indices During Routine Clinical Procedures
Acronym:	PRESSUREwire
Purpose:	
The purpose of this study is to understand routine use of FFR and alternate indices in clinical practice. This study will determine the use and clinical outcome of FFR-guided PCI in patients presenting with either stable coronary artery disease, or in patients presenting with Acute Coronary Syndrome (ACS) on culprit and non-culprit lesions as well as during index and secondary procedures.
 
The study will also collect data on the routine use of coronary physiologic measurements such as adenosine-induced hyperemia FFR, FFR by contrast-induced hyperemia, Pd/Pa, and other alternate indices measurements.

Objectives:	
All objectives will be evaluated for all subjects enrolled, ACS subjects and stable coronary artery disease subjects separately.
 
 1. Characterize the frequency of change in treatment plan when FFR is used compared to the initial decision based on angiography alone. 2. Characterize the 12 month clinical outcomes (MACE) in subjects in whom the use of FFR did not lead to a change in treatment decision vs subjects in whom the use of FFR led to a change in treatment decision. 3. Characterize the 12 month clinical outcomes (MACE) by FFR values and resting indices respectively. 4. Compare resting indices with FFR values. 5. Characterize the 12 month clinical outcomes (MACE) by other PressureWire-derived indices (coronary flow reserve (CFR), index of microcirculatory resistance (IMR), contrast FFR, resistance reserve ratio (RRR)). 6. Compare other PressureWire-derived indices (CFR, IMR, contrast FFR, RRR) with FFR values.
Design:	
This study is a prospective, multicenter, multinational, multicontinental open label observational study.
 
The total duration of the study is expected to be 4 years, which includes 3 years for enrollment with 12 months of follow-up.
 
The clinical study will be conducted in approximately 200 centers globally.

Clinical Investigational Plan

Sample Size and Planned Analysis	This is an observational study. No formal power analysis and sample size calculations were performed. Approximately 2000 subjects will be enrolled in this study. No single center is allowed to enroll more than 10% of the population. A target of 500 ACS patients will be included in the study. This sample size allows reasonable enrollment to detect a signal from events at 12 months.
Devices used:	Any commercially available St. Jude Medical PressureWire™ may be used for this study.
Study Population	
A patient becomes a subject (enrolled) once he/she has been fully informed about the study, has agreed to participate, signed & dated the consent, has been determined to meet all inclusion criteria and none of the exclusion criteria, and at least one physiologic coronary pressure measurement with an SJM PressureWire™ has been recorded.
 
Since this study is a routine clinical practice observational study, patients are allowed to be consented after the procedure, but must be consented prior to any data submission.
 
Specific study population characteristics are defined as follows:
 
Patients where FFR has been performed or is planned to be performed for further evaluation of PCI procedures, as per physician clinical practice.

Inclusion/Exclusion Criteria	
Inclusion/Exclusion is defined as follows:
 
Inclusion Criteria:
 
 1. Patient is presenting with STEMI, NSTEMI, unstable angina, or stable coronary artery disease 2. Patient is planned to have FFR performed or underwent a cardiac catheterization where FFR was performed for further PCI consideration 3. Patient signs and dates written informed consent 4. Patient is eighteen years of age or older at the time of consent 
Exclusion Criteria:
 
 1. Patient has extremely tortuous or calcified coronary arteries 2. Patient with a patent coronary artery bypass graft to the target vessel
Data Collection	Data collection will be comprised of baseline demographics and medical history, coronary anatomy, procedure, discharge, and 1 year follow up phone call for MACE events.
Publication of Data	Data is planned to be analyzed and released at enrollment intervals of 500, 1000, 1500, and 2000.

Clinical Investigational Plan

1.1 STUDY ASSESSMENT SCHEDULE

	Baseline	Procedure	Discharge	One Year* (± 30 days)	Interim Visit (Subject with potential MACE event)
Medical History, Demographics and Current Clinical Status	X				
Angiography and PCI procedure Details		X			
Coronary Physiologic Measurements		X**			
MACE Assessment		X	X	X	X
Medication Assessment	X		X	X	X

*Visit may be conducted via a phone call

**May occur at index or secondary procedures for patients presenting with ACS

2.0 BACKGROUND AND JUSTIFICATION FOR CLINICAL STUDY

Fractional flow reserve (FFR) has been demonstrated to be an effective index for determining percutaneous coronary intervention (PCI) approach. FFR is defined as the ratio of maximum blood flow in a stenotic coronary artery to maximum blood flow if the same artery were completely normal. An FFR of 0.80 or less, as measured with the use of a coronary pressure wire during invasive coronary angiography, indicates the potential of a specific stenosis to induce myocardial ischemia with an accuracy of greater than 90%. Therefore, FFR is recommended for the guidance of coronary revascularization.¹

Randomized clinical trials have demonstrated that in patients with unstable angina and acute myocardial infarction (MI), there are substantial benefits of PCI, including prevention of myocardial infarction and reduced mortality rate.^{2,3} In patients with stable coronary artery disease (CAD), PCI has been shown to improve anginal symptoms and quality of life. The FAME (Fractional Flow Reserve Versus Angiography for Multivessel Evaluation) 2 year data showed that in patients with multivessel CAD undergoing PCI with drug-eluting stents, routine measurement of FFR as compared with PCI guided by angiography alone resulted in a significant reduction of the rate of mortality and myocardial infarction.⁴

Currently, there has been limited research conducted on the use of FFR in ACS patients. According to Depta, “a recent study determined that vasodilatory capacity of the microcirculation was similar between patients with non-ST elevation myocardial infarction and stable angina. Thus, FFR measurement during ACS or AMI may be reliable”.⁵ While clinical evidence in this setting remains sparse and non-conclusive, FFR use in ACS patients is expanding and more research needs to be conducted.⁶ However, recent trials suggest increasing evidence that supports the role of FFR-guided strategy in ACS patients.⁷

For example, Leite notes that, “One of the most important studies about the use of FFR in ACS was from Ntalanis et al.⁸ who studied 75 acute STEMI patients and 26 NSTEMI patients (<72 h post onset) and measured FFR in the non-culprit stenosis immediately following PCI of the culprit vessel and then repeated the FFR at 35 + 4 days post initial procedure. The FFR value remained unchanged between the acute and follow-up phases in patients with STEMI (0.78 + 0.10 vs. 0.77 + 0.20, p = NS). In only 2 patients, the FFR value was higher than 0.80 at the acute phase and lower than 0.75 at follow-up. The authors stated the data supports that FFR measurements are safe and reliable for evaluating the severity of non-culprit stenosis in the acute phase of ACS, even during primary PCI.”⁹

Alternative indices utilizing pressure wires have also become important to understanding the physiologic significance of coronary artery disease.¹⁰ Adenosine-induced hyperemia FFR, Pd/Pa, FFR by contrast-induced hyperemia, coronary flow reserve (CFR), the index of microcirculatory resistance (IMR), as well as other novel indices e.g. resistance reserve ratio (RRR), potentially aid in treatment decisions of patients with CAD.

To date, there has not been a large registry study analyzing the use of FFR and alternate indices in everyday practice. The PRESSUREwire study looks to expand on the current evidence by collecting additional data on the use and clinical outcome of FFR-guided PCI in patients presenting with stable coronary artery disease, patients presenting with ACS, as well as those who received routine coronary physiologic measurements of adenosine-induced hyperemia FFR, Pd/Pa, FFR by contrast induced hyperemia, and other alternate indices measurements.

Clinical Investigational Plan

The PRESSUREwire study is an observational study intending to collect additional data on the use and clinical outcome of FFR-guided PCI patients presenting with Acute Coronary Syndrome (ACS) on culprit and non-culprit lesions at index and secondary procedures.

3.0 STUDY DESIGN

3.1 PURPOSE

The purpose of this clinical study is to understand routine use of FFR and alternate indices in clinical practice in the treatment of subjects presenting with either an Acute Coronary Syndrome (ACS) or stable coronary artery disease.

3.2 STUDY DESIGN AND SCOPE

This study is a prospective, multicenter, multinational, multicontinental open label observational study.

This study will determine the use and clinical outcome of FFR-guided PCI on patients presenting with either stable coronary artery disease or ACS both for culprit and non-culprit lesions as well as during index and secondary procedures.

The FFR threshold for decision making is anticipated to be 0.80 in line with contemporary guidelines. Since the study is observational, there are no mandated thresholds for any of the physiologic measurements.

The study will also collect data on the routine use of coronary physiologic measurements such as adenosine-induced hyperemia FFR, FFR by contrast-induced hyperemia, Pd/Pa, and other alternate indices measurements.

The total duration of the study is expected to be 4 years, which includes 3 years for enrollment with 12 months of subject follow-up.

The clinical study will be conducted in approximately 200 centers in North America, EMEA, and Asia Pacific.

3.2.1 Number of subjects required

Up to 2000 subjects will be enrolled in this study. No single center is allowed to enroll more than 10% of the population. A target of 500 ACS patients will be included in the study.

3.3 OBJECTIVES

All objectives will be evaluated for all subjects enrolled, ACS subjects and stable coronary artery disease subjects separately.

1. Characterize the frequency of change in treatment plan when FFR is used compared to the initial decision based on angiography alone.
2. Characterize the 12 month clinical outcomes (MACE) in subjects in whom the use of FFR did not lead to a change in treatment decision vs subjects in whom the use of FFR led to a change in treatment decision.

Clinical Investigational Plan

3. Characterize the 12 month clinical outcomes (MACE) by FFR values and resting indices respectively.
4. Compare resting indices with FFR values.
5. Characterize the 12 month clinical outcomes (MACE) by other PressureWire-derived indices (coronary flow reserve (CFR), index of microcirculatory resistance (IMR), contrast FFR, resistance reserve ratio (RRR)).
6. Compare other PressureWire-derived indices (CFR, IMR, contrast FFR, RRR) with FFR values.

Refer to section 12.0 for statistical analysis.

3.4 INCLUSION AND EXCLUSION CRITERIA

A subject, who meets all of the inclusion criteria, and none of the exclusion criteria, is eligible to participate in this study.

All subjects enrolled in the clinical study (including those withdrawn from the clinical study or lost to follow-up) will be accounted for and documented, assigning an identification code.

3.4.1 Inclusion Criteria

1. Patient is presenting with STEMI, NSTEMI, unstable angina, or stable coronary artery disease
2. Patient is planned to have FFR performed or underwent a cardiac catheterization where FFR was performed for further PCI consideration
3. Patient signs and dates written informed consent
4. Patient is eighteen years of age or older at the time of consent

3.4.2 Exclusion Criteria

1. Patient has extremely tortuous or calcified coronary arteries
2. Patient with a patent coronary artery bypass graft to the target vessel

3.5 SUBJECT POPULATION

3.5.1 Subject Screening

Potential subjects presenting at the investigational site will be screened by a member of the investigational team previously trained on the CIP and delegated to do so.

Subjects who do not meet the inclusion/exclusion criteria will not be eligible to participate in this study.

Subjects meeting the inclusion/exclusion criteria will be fully informed about the study and asked to participate in the study. In case the subject agrees, a duly signed and dated Patient Informed Consent will be obtained.

3.5.2 Point of Enrollment

A patient becomes a subject (enrolled) once he/she has been fully informed about the study, has agreed to participate, signed & dated the consent, has been determined to meet all inclusion criteria

Clinical Investigational Plan

and none of the exclusion criteria, and at least one physiologic coronary pressure measurement with an SJM PressureWire™ has been recorded. Refer to section 3.6 for the Informed Consent Process.

3.6 INFORMED CONSENT PROCESS

3.6.1 General process

Prior to enrolling in the clinical study, all subjects will be consented, as required by applicable regulations and the center's IRB/EC. Informed consent must be obtained from each subject prior to any data collection. The consent form must be signed and dated by the subject and by the person obtaining the consent.

Medical circumstances may occur where potential subjects require emergent medical intervention, and thus measurements of their FFR and other metrics (i.e. patients experiencing ACS). As a result, and since this is a routine clinical practice observational study, subjects are allowed to be consented after the procedure, but must be consented prior to any data submission.

The Principal Investigator or his/her authorized designee will conduct the Informed Consent Process. This process will include a verbal discussion with the subject on all aspects of the clinical study that is relevant to the subject's decision to participate in the clinical study.

The subject shall be provided with the informed consent form that is written in a language that is understandable to the subject and has been approved by the center's IRB/EC. Failure to obtain informed consent from a subject prior to study enrollment should be reported to St. Jude Medical within 5 working days and to the reviewing center's IRB/EC consistent with the center's IRB/EC reporting requirements.

4.0 RISKS AND BENEFITS OF THE CLINICAL STUDY

4.1 ANTICIPATED CLINICAL BENEFITS

This is a prospective observational study of market-released products. The potential benefit of participating in this study with standard of care treatment is that data from this study may enhance future treatment for PCI patients.

There are no direct benefits from participating in the study.

4.2 ANTICIPATED ADVERSE EVENTS AND ADVERSE DEVICE EFFECTS

This is a prospective observational study of market-released products. Anticipated adverse events or adverse device effects are the same whether the subject receives the assessment as part of the study or outside of the study.

4.3 RISKS ASSOCIATED WITH PARTICIPATION IN THE CLINICAL STUDY

The risks of taking part in the PRESSUREwire study and undergoing FFR assessment or alternative indices are the same whether the subject receives the assessment as part of the study or outside of the study.

Clinical Investigational Plan

Refer to the Instructions for Use (IFU) in the package labeling for potential risks associated with an SJM PressureWire™.

A risk of study participation is that confidentiality cannot be guaranteed. Investigational site personnel, SJM, and SJM representatives will take measures to de-identify study subject personal health information in an effort to maintain subject anonymity.

5.0 DEVICE UNDER INVESTIGATION

5.1 DEVICE DESCRIPTION

Only market-released products will be used in this study. No comparisons are being made between devices.

St. Jude Medical pressure wires are guidewires with integrated sensor elements at the tip to enable measurements of physiological parameters. These guidewires are uniquely paired with specific transmitters and are available in different lengths.

[figure not shown]
These guidewires are designed to fit inside a percutaneous catheter for the purpose of directing the catheter through a vessel. The signal output from the sensor is transmitted to associated equipment for analysis, used for calculations, and presentation display of physiological parameters functions or indices based on pressure or temperature, e.g. Fractional Flow Reserve (FFR).

Only a commercially available St. Jude Medical PressureWire™ may be utilized for this study.

6.0 PROCEDURES

6.1 STUDY FLOW CHART

Figure 1: Procedural Flow Chart

*ADO FFR – IV or IC adenosine, or another suitable agent (Appendix B), for FFR

6.2 PROCEDURES

The clinical study will be conducted in accordance with the CIP. All parties participating in the conduct of the clinical study will be qualified by education, training, or experience to perform their tasks and this training will be documented appropriately.

The clinical study will not commence until St. Jude Medical receives written approval from the IRB/EC and relevant regulatory authorities and all required documents have been collected from the site(s).

Clinical Investigational Plan

Table 1: List of all study specific activities/procedures

	Baseline	Procedure	Discharge	One Year* (± 30 days)	Interim Visit (Subject with potential MACE event)
Medical History, Demographics and Current Clinical Status	X				
Angiography and PCI procedure Details		X			
Coronary Physiologic Measurements		X**			
MACE Assessment		X	X	X	X
Medication Assessment	X		X	X	X

*Visit may be conducted via a phone call

**May occur at index or secondary procedures for patients presenting with ACS

A lesion >50% severity by angiographic assessment is considered to be clinically significant.

6.3 BASELINE VISIT

The following enrollment activities are performed after the subject has been screened and may occur before or after the study procedure/visit.

- The principal or delegated study personnel determine subject eligibility for the study
- Record enrollment information (name of the study, date of consent and inclusion/exclusion information) in the hospital records and complete and submit the Enrollment form in a timely manner (recommended within 5 days)
- Notification of a consented subject to the sponsor will take place when the sponsor receives the baseline form

If a subject does not meet all inclusion criteria or meets any of the exclusion criteria, the subject cannot participate in the study and cannot be enrolled.

In case the subject was already consented to participate in the study and an FFR was performed, and it was determined that they do not meet inclusion/exclusion criteria, the following actions will be taken:

- Document enrollment information (name of the study, date of consent and inclusion/exclusion) in the hospital records; complete the Baseline and Withdrawal Forms. The form(s) must be authorized / approved by the principal or delegated investigator.
 - Inform the subject about the withdrawal.
 - The EC/IRB and Competent Authority should be notified appropriately, as per local regulations, about any deviations with regards to obtaining the informed consent.

The following information will be collected at the baseline visit:

- Medical history
- Demographics- include subject's Year of Birth and Gender
- Current clinical status

Clinical Investigational Plan

6.4 PROCEDURE

Refer to the Instructions For Use (IFU) for procedural steps.

Fractional Flow Reserve (FFR) is an index determining the functional severity of narrowing(s) in the coronary arteries. FFR specifically identifies which coronary narrowing(s) are responsible for significantly obstructing the flow of blood to the heart muscle. FFR is used in conjunction with cardiac catheterization by placing the pressure wire distal to the coronary lesion and measuring pressure inside the artery. The pressure wire is then retracted until pressure is measured in the entire coronary artery.

The following data points will be collected during the procedure for all evaluated lesions (index or secondary procedures):

- Measurements of Pd/Pa
- Measurements of FFR with Adenosine induced hyperemia (IC or IV)
- MACE assessment (required)
- Prospective treatment decisions; initial treatment plan documentation shall be prior to FFR.

Other indices may be collected, according to the investigator's clinical practice and availability of appropriate devices (index or secondary procedures), as follows;

- IMR measurements
- CFR measurements
- Measurements of FFR with Contrast induced hyperemia
- Measurements of any additional novel resting indices (RI)

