12.1.3 Statistical Method and Analysis

This section describes the statistical method and analysis per subject basis unless otherwise specified. If more than one lesion is measured for a subject, the data analysis may be performed and presented on a per lesion basis, as appropriate.

The following criteria will be used to define the variables per subject level for subject with multiple lesions:

- Treatment decision is defined as “changed” if there is at least one decision change based on FFR for multiple lesions; if none of the decisions has been changed for the multiple lesions, the treatment decision is defined as “unchanged”.
- For all the continuous variables of FFR, resting indices, CFR, contrast FFR, and RRR, we will use the lowest value in all lesions as the value for that variable in each subject. For the continuous variable of IMR, we will use the highest value in all lesions as the value for IMR in each subject.

The following cutoff values will be used to categorize a continuous variable into a binary variable:

- FFR group is defined as “low FFR” if it is equal to or below 0.8 (the cutoff value of 0.8 is selected in line with contemporary guidelines and previous findings¹¹). However, since this is an observational study, there are no mandated cutoff values for this. Therefore, we will also use cutoff value of 0.75¹² in the analysis.
- Resting indices group is defined as “low resting indices” if it is equal to or below 0.86 (the cutoff value of 0.86 is selected based on previous findings that a baseline Pd/Pa \leq 0.86 is associated with a positive predictive value of 100% for FFR measurement¹³). We will also use the cutoff value of 0.92¹⁴ in the analysis.

Clinical Investigational Plan

- CFR is defined as “low CRF” if it is below 2.0 (the cutoff value of 2.0 is selected based on previous findings^{15,16}).
- IMR is defined as “high IMR” if it is equal to or above 25 (the cutoff value of 25 is selected based on previous findings¹⁷).
- Contrast FFR is defined as “low Contrast FFR” if it is equal to or below 0.83 (the cutoff value of 0.83 is selected based on previous findings¹⁸).
- RRR is defined as “low RRR” if it is smaller than 2.0 (the cutoff value of 2.0 is selected based on previous findings¹⁹).

The following statistical analysis will be performed for each of the study objectives:

1. Characterize the frequency of change in treatment plan when FFR is used compared to the initial decision based on angiography alone

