Frequency and percentage of change in treatment decisions when FFR is used compared to the initial decision based on angiography alone will be presented both per subject level and per lesion level.

2. Characterize the 12-month clinical outcomes (MACE) in subjects in whom the use of FFR did not lead to a change in treatment decision vs. subjects in whom the use of FFR led to a change in treatment decision.

12-month MACE event rate will be summarized using frequency and percentage. Fisher Exact test will be performed to evaluate the association between 12-month MACE event and prospective treatment decisions, i.e. change or no change, based on FFR measurements. A repeated measures logistic regression with generalized estimating equations (GEE) per lesion level will be performed if needed.

3. Characterize the 12 month clinical outcomes (MACE) by FFR values and resting indices respectively.

Fisher Exact test will be performed to evaluate the association between 12-month MACE event and binary FFR and binary resting indices variables respectively using the following FFR and resting indices groups:

- 1) Low FFR group ($FFR \leq 0.8$) and high FFR group ($FFR > 0.8$).
- 2) Low FFR group ($FFR < 0.75$) and high FFR group ($FFR \geq 0.75$).
- 3) Low resting indices group ($Pd/Pa \leq 0.86$) and high resting indices group ($Pd/Pa > 0.86$).
- 4) Low resting indices group ($Pd/Pa \leq 0.92$) and high resting indices group ($Pd/Pa > 0.92$).

A repeated measures logistic regression with generalized estimating equations (GEE) per lesion level will be performed if needed.

A logistic regression will be performed to evaluate the association between 12-month MACE event and continuous FFR and continuous resting indices respectively. A repeated measures logistic regression with generalized estimating equations (GEE) per lesion will be performed if needed.

4. Compare resting indices with FFR values.

Kappa coefficient will be used for binary variables, and correlation will be used for continuous variables to examine agreement between FFR values and resting indices.

5. Characterize the 12 month clinical outcomes (MACE) by other PressureWire-derived indices (CFR, IMR, contrast FFR, RRR).

Clinical Investigational Plan

Fisher Exact test will be used for binary variables, and logistic regression will be used for continuous variables to evaluate the association between 12-month MACE event and other PressureWire-derived indices (CFR, IMR, contrast FFR, RRR) respectively.

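### Section 6.4 ties the initial treatment plan to FFR rather than to the first pressure-wire reading, so the angiographic decision that Objective 1 needs may already reflect Pd/Pa or another lesion's FFR

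*Combined protocol and SAP*

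**What the plan says.** Section 3.3 gives Objective 1 as: "Characterize the frequency of change in treatment plan when FFR is used compared to the initial decision based on angiography alone". Section 12.1.3 keeps the same reference point and makes the analysis descriptive: "Frequency and percentage of change in treatment decisions when FFR is used compared to the initial decision based on angiography alone", reported per subject and per lesion. A subject counts as changed if the decision changed for at least one lesion. The same change/no-change variable is the grouping factor in the Fisher exact test of 12-month MACE under Objective 2.

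The only operational timing instruction in the available text is in the section 6.4 list of data points: "Prospective treatment decisions; initial treatment plan documentation shall be prior to FFR". That list covers all evaluated lesions, at index or secondary procedures, and has "Measurements of Pd/Pa" as an item separate from adenosine FFR. Among the optional items is "Measurements of FFR with Contrast induced hyperemia".

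Section 12.1.3 also treats FFR and resting indices as different variables with different cutoffs (0.80 and 0.75 for FFR; 0.86 and 0.92 for Pd/Pa). It justifies 0.86 by saying that a baseline Pd/Pa at or below that value "is associated with a positive predictive value of 100% for FFR measurement".

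**The concern.** The objective and the rule refer to two different moments. The objective needs the decision as it stood after angiography. The rule needs only that the plan be written before FFR. Between the two, the wire can be in place and a resting Pd/Pa visible. An operator who has seen that value is no longer deciding on the angiogram only, and for low values the protocol itself describes Pd/Pa as highly informative about FFR. In a patient with several lesions, the plan for a later lesion can likewise be written when the FFR of an earlier one is known.

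If the operator changes course because of such a reading and then writes the plan, the subject is coded as unchanged although the wire changed the decision. This affects the Objective 1 frequency directly, and it moves subjects between the groups compared in Objective 2. Monitoring for protocol deviations would not find it, because the written rule has been met. Without a recorded sequence it cannot be corrected at the analysis stage.

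**Working it through.** **Step 1: what the rule allows.** The plan states no expected change rate and has no sample size calculation (section 12.1.1), so there is no figure to reproduce. The check starts from the text.

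- Reference decision: angiogram only (sections 3.3 and 12.1.3).
- Timing anchor: before FFR (section 6.4).
- Pd/Pa: required in every evaluated lesion and listed apart from FFR (section 6.4). Objective 4 compares resting indices with FFR, and section 12.1.3 gives them separate definitions.
- Recording of sequence, or hiding Pd/Pa from the operator: not mentioned in the available text.
- Several lesions: nothing says that all plans must precede the first reading in any lesion.

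In the study's own vocabulary, a plan written after Pd/Pa and before FFR therefore meets the rule without meeting the objective.

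**Step 2: an illustration of size.** All four inputs are assumptions; none comes from the documents.

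- c = true rate of change from the angiographic decision to the FFR-based decision
- f = share of plans written after a wire reading
- g = share of true changes already absorbed into those plans
- h = share of true non-changes that the early reading makes discordant with the final decision

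Observed rate = c(1 − f·g) + (1 − c)·f·h

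With c = 30%, g = 50%, h = 5%:

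| f | Calculation | Observed | Error (points) |
|---|---|---|---|
| 0% | 0.30 | 30.0% | 0 |
| 10% | 0.30 × 0.95 + 0.70 × 0.005 = 0.2885 | 28.9% | −1.15 |
| 25% | 0.30 × 0.875 + 0.70 × 0.0125 = 0.27125 | 27.1% | −2.9 |
| 50% | 0.30 × 0.75 + 0.70 × 0.025 = 0.2425 | 24.3% | −5.75 |
| 100% | 0.30 × 0.50 + 0.70 × 0.05 = 0.185 | 18.5% | −11.5 |

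95% half-width = 1.96 × √(0.30 × 0.70 / n): 2.0 points at n = 2000, and 4.0 points at n = 500 (the ACS target). On these inputs the error passes the sampling error of the full cohort by about f = 25%.

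**Step 3: the direction.** The rate is understated only if c·g > (1 − c)·h. At c = 30% and g = 30%, break-even is h = 0.09 / 0.70 = 12.9%. At c = 20%, g = 30%, h = 15%, f = 50%, the observed rate is 0.20 × 0.85 + 0.80 × 0.075 = 23%, which is 3 points too high.

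**Step 4: Objective 2.** On the Step 2 inputs with f = 50%, absorbed changes are 0.30 × 0.50 × 0.50 = 7.5% of subjects. The observed unchanged group is 1 − 0.2425 = 75.75%, so 7.5 / 75.75 = 9.9% of it was truly changed. Spurious changes are 0.70 × 0.50 × 0.05 = 1.75%, or 1.75 / 24.25 = 7.2% of the observed changed group. At f = 25% the two shares are 3.75 / 72.875 = 5.1% and 0.875 / 27.125 = 3.2%.

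**The case against.** The strongest reply is that the protocol read as a whole already says what is meant. Objective 1 tells sites that the comparator is the angiographic decision, and section 6.2 requires trained staff to follow the plan. Section 6.4 also uses FFR for the whole wire procedure: "FFR is used in conjunction with cardiac catheterization by placing the pressure wire distal to the coronary lesion". On that reading, before FFR means before the wire. In addition, Figure 1, the procedural flow chart, is not reproduced in the available text, and the case report forms are under separate cover (Appendix G). Either may fix the order.

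Much of this stands. It makes the rule ambiguous rather than plainly wrong, and it is why the point is conditional on the figure and the forms. It does not remove the gap, because the objectives, the data list and the cutoffs all treat resting indices and FFR as distinct, and about 200 centers may settle the ambiguity differently. Nor does a broad reading clearly settle the order across several lesions.

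Three stronger readings are tempting, and the documents do not support them.

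- A reader might infer that the rule also lets a plan be written after contrast FFR. Section 6.4 names that measurement as a form of FFR, so such a plan is hard to call prior to FFR. It is also optional.
- A reader might infer from the 100% predictive value that most changes are settled before FFR. That figure concerns only lesions at or below 0.86, and their share is not given.
- A reader might infer that the change rate is known to be understated. Nothing shows that any plan is written after a reading.

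**Conclusion.** The written rule does not secure the comparator that Objectives 1 and 2 need. A compliant plan can already reflect resting Pd/Pa or the FFR of another lesion, unless Figure 1 or the case report form prevents it. The likely effect is a change rate that is too low and change/no-change groups that are partly misclassified. Neither the direction nor the size is established. The error is zero if no plan follows a reading, and an overstatement is possible if early readings often produce plans that FFR then reverses. The figures of 27.1% and 24.3% against a true 30% show only that the error could exceed the 2.0-point half-width. They rest wholly on assumed inputs, treat each subject as one decision, and are not an estimate for this study. This is a cheap improvement: a small change to a stated rule that guards against an error which cannot be undone later.

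**What to change.** Reword section 6.4 so that the initial plan for every lesion to be evaluated is documented from the angiogram before any pressure-wire reading in any lesion of that procedure. If Figure 1 already shows this order, bring the text into line with it. Add one eCRF field, either yes/no or a time stamp, recording whether this was met.

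Report Objectives 1 and 2 for all subjects as planned, and add a sensitivity analysis restricted to plans recorded before the first wire reading. The restricted set should not become the main analysis, because it would select subjects by operator workflow.

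The cost is one sentence, one field and one extra table. The change concerns the order of documentation and mandates no treatment. Two limits remain. Section 3.6.1 allows consent after the procedure, so the field may sometimes be completed retrospectively. And a plan made at a secondary procedure may still follow readings from the index procedure, which the report should state.
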